9.1 Adverse Events

All adverse events will be coded by System Organ Class (SOC) and Preferred Term (PT) according to the Medical Dictionary for Regulatory Activities (MedDRA). AEs that are sex-specific, e.g., ovarian cancer, will have their incidence rates evaluated for the specific sex.

Treatment-emergent AEs (TEAEs) are defined as AEs with an onset date on or after the first dose of IMP. In more detail, TEAEs are all adverse events which started after start of IMP; or if the event was continuous from baseline and was worsening, serious, study drug related, or resulted in death, discontinuation, interruption or reduction of study therapy. Adverse events occurring up to 30 days after the last day of IMP will be included in the summary tables.

The incidence of the following events in the open-label treatment phase will be tabulated by treatment group and overall using the Safety Sample:

- a) TEAEs
- b) TEAEs by severity
- c) TEAEs potentially causally related to the IMP
- d) TEAEs with an outcome of death
- e) Serious TEAEs
- f) TEAEs leading to discontinuations of the IMP
- g) AESI

The above summaries (b), (e) and (f) will also be prepared for TEAEs potentially causally related to the IMP.

In addition, incidence of TEAE during the open-label treatment phase of at least 5% by SOC and PT will be provided.

Incidence of TEAEs by SOC and PT will be summarized for sex, race, age and region subgroups.

Extrapyramidal symptoms (EPS)-related AEs will be grouped into five categories.

- 1) Dystonic Events, which include cervical spasm, dystonia, emprosthotonus, muscle contractions involuntary, muscle rigidity, muscle spasms, muscle spasticity, myotonia, nuchal rigidity, oculogyration, opisthotonus, pleurothotonus, risus sardonicus, torticollis, and trismus;
- 2) Parkinsonian Events, which include akinesia, asterixis, athetosis, bradykinesia, cogwheel rigidity, essential tremor, extrapyramidal disorder, freezing phenomenon, gait festinating, hypertonia, hypokinesia, hypokinesia neonatal, intention tremor, masked facies, parkinson's disease, parkinsonian crisis, parkinsonian gait, parkinsonian rest tremor, parkinsonism, tremor, and tremor neonatal;
- 3) Akathisia Events, which include akathisia, hyperkinesia, and psychomotor hyperactivity;
- 4) Dyskinetic Events, which include ballismus, buccoglossal syndrome, choreoathetosis, clumsiness, dyskinesia, dyskinesia neonatal, dyskinesia oesophageal, fumbling, nodding of head, on and off phenomenon, and tardive dyskinesia;
- 5) Residual Events, which include chorea, Huntington's chorea, muscle twitching, and myoclonus.

Adverse Events of Special Interest

The new onset or exacerbation of “Pathological Gambling and Other Compulsive Behaviors” will be analyzed as an AESI.

Unless otherwise specified, in general, analysis of safety data will be performed on observed case and for last visit.

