Assessments for Safety: Adverse event (AE) reporting, clinical laboratory tests (including prolactin and glycosylated hemoglobin [HbA1c]), electrocardiogram (ECG), vital signs, physical examination, Simpson Angus Scale (SAS), Abnormal Involuntary Movement Scale (AIMS), Barnes Akathisia Rating Scale (BARS), and Columbia-Suicide Severity Rating Scale (C-SSRS).

Screening/Other: Medical, psychiatric, and medication history; urine drug and blood alcohol screening; and urine pregnancy test.

Data Monitoring Committee: None.

Statistical Methods:

The sample size is not based on statistical power considerations but on the number of subjects rolling over from the lead-in trials. The trial population will be derived from eligible subjects who completed the previous double-blind brexpiprazole BPD trials. The number of eligible subjects will be limited by the number of subjects enrolled into the double-blind trials.

The primary safety analysis is the frequency and severity of AEs in the open-label treatment phase. All AEs will be coded by system organ class and the Medical Dictionary for Regulatory Activities preferred term. The incidence of the following events will be summarized by the prior treatment group:

- 1) Treatment-emergent adverse events (TEAEs)
- 2) TEAEs by severity,
- 3) TEAEs potentially causally related to the IMP,
- 4) TEAEs with an outcome of death,
- 5) Serious TEAEs,
- 6) TEAEs leading to discontinuation of the IMP,
- 7) Adverse events of special interest (AESI).

A TEAE is defined as an AE that starts after the first dose of IMP or an AE that is reported at baseline and increases in intensity or becomes serious or IMP-related or results in death, discontinuation, interruption or reduction of IMP. Information about new onset or exacerbation of “Pathological Gambling and Other Compulsive Behaviors” will be collected and analyzed as an AE of special interest.

Complete details of the planned statistical analysis will be presented in the statistical analysis plan.

[figure not shown]
Trial Duration:

Each subject in this trial is expected to participate in the following periods of the trial (approximate durations listed), for approximately 15 weeks:

- Eligibility screening period (1 day) (If a subject is unable to rollover immediately, up to 3 days may be permitted between the end of the double-blind trial and the start of IMP in the open-label extension trial; however, this must be discussed with the medical monitor.)

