8.8 Adverse Events

8.8.1 Definitions

An AE is defined as any untoward medical occurrence in a clinical trial subject administered an IMP and which does not necessarily have a causal relationship with this treatment. Adverse events would not include information recorded as medical history at screening/baseline for pre-planned procedures for which the underlying condition was known and no worsening occurred. An adverse reaction is any untoward and unintended response to an IMP related to any dose administered.

A suspected adverse reaction is any AE for which there is a reasonable possibility that the IMP caused the AE. For the purpose of IND safety reporting, “reasonable possibility” means there is evidence to suggest a causal relationship between the IMP and the AE. Suspected adverse reaction implies a lesser degree of certainty about causality.

Treatment-emergent AEs are defined as AEs with an onset date on or after the start of open-label treatment. In more detail, TEAEs are all AEs which started after start of open-label IMP treatment; or if the event was continuous from baseline and was worsening, serious, IMP related, or resulted in death, discontinuation, interruption or reduction of IMP.

An SAE includes any event that results in any of the following outcomes:

- Death
- Life-threatening; ie, the subject was, in the opinion of the investigator, at immediate risk of death from the event as it occurred. It does not include an event that, had it occurred in a more severe form, might have caused death.
- Persistent or significant incapacity/disability or substantial disruption of the ability to conduct normal life functions.
- Requires inpatient hospitalization or prolongs hospitalization.
 - Hospitalization itself should not be reported as an SAE; whenever possible the reason for the hospitalization should be reported.
 - Hospitalizations or prolonged hospitalizations for social admissions (ie, those required for reasons of convenience or other nonmedical need) are not considered SAEs.
 - Prescheduled hospitalization to address a condition that has existed prior to the signing of the ICF should not be considered an SAE.
- Congenital anomaly/birth defect.

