9.4.2.1 Adverse Events

All AEs will be coded by system organ class and Medical Dictionary for Regulatory Activities preferred term. The incidence of the following events will be summarized by the prior treatment group:

- Treatment-emergent AEs (TEAEs)
- TEAEs by severity
- TEAEs potentially causally related to the IMP
- TEAEs with an outcome of death
- Serious TEAEs
- TEAEs leading to discontinuation of the IMP
- AESI

A TEAE is defined as an AE that starts after the first dose of IMP or an AE that is reported at baseline and increases in intensity or becomes serious or IMP-related or results in death, discontinuation, interruption or reduction of IMP. Information about new onset or exacerbation of “Pathological Gambling and Other Compulsive Behaviors” will be collected and analyzed as an AE of special interest.

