Table 3.2-1 Dosing Schedule**Error! Bookmark not defined.**

List of In-text Figures

Figure 3.1-1	Trial Design Schematic	8
--------------	------------------------------	---

1 Introduction

This statistical analysis plan (SAP) documents the statistical methodology and data analysis algorithms and conventions to be applied for statistical analysis and reporting of efficacy and safety data of study 331-201-00195. All amendments and addendums to the protocol are taken into consideration in developing this SAP. In addition, if the analyses described in the protocols differ from those in this SAP, the methods of the SAP prevail.

2 Study Objectives

Primary Safety: To evaluate the safety and tolerability of brexpiprazole for the treatment of subjects with a diagnosis of BPD.

3 Trial Details

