3.1 Study Design

This is a 12-week, multicenter, open-label trial designed to evaluate the safety and tolerability of brexpiprazole treatment in adult subjects diagnosed with BPD. Subjects will receive 2 to 3 mg/day brexpiprazole.

Enrollment into the trial will be drawn from eligible subjects who completed the last treatment visit of the previous double-blind brexpiprazole BPD trials (and took the investigational medicinal product [IMP] through the last scheduled treatment visit) and, in the investigator's judgment, could potentially benefit from treatment with brexpiprazole for BPD.

The trial will be organized as follows:

[figure not shown]
Screening/Baseline: Subjects will be screened for eligibility at the last scheduled treatment visit of the previous double-blind trial. Subjects will sign a separate informed consent form (ICF) at the last scheduled treatment visit of the previous double-blind trial for participation in this trial before any procedures specific to the open-label trial are performed. The assessments from the last scheduled treatment visit of the previous double-blind trial will serve as the baseline measures for this trial for any assessment that is not new (unique) to the open-label trial. Medical history will be updated, if necessary. Informed consent cannot be obtained after the last scheduled treatment visit of the previous double-blind trial without all screening/baseline assessments being repeated. If a subject is unable to rollover immediately, up to 3 days may be permitted between the end of the double-blind trial and the start of IMP in the open-label extension trial; however, this must be discussed with the medical monitor (Note: assessments from the last scheduled treatment visit in the previous double-blind trial that are going to be used as the baseline measures for Trial 331-201-00195 will not need to be repeated if the subject enters Trial 331-201-00195 within 3 days).

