Due to COVID-19, delayed entry subjects are permitted to be screened for Trial 331-201-00195 up to 90 days after completing the last scheduled treatment visit of the previous double-blind BPD trial (discussion with the medical monitor is required if > 90 days have passed). These subjects will be screened for eligibility at a separate screening visit for Trial 331-201-00195, where they will undergo full assessments to determine eligibility. The screening period will be up to 21 days and may be extended upon discussion with the medical monitor. The delayed entry subjects will also undergo a separate baseline visit, and the assessments from that visit will serve as the baseline measures for Trial 331-201-00195. Delayed entry subjects will receive the first dose of IMP at the baseline visit.

Treatment Phase: Eligible subjects will receive daily treatment with open-label brexpiprazole beginning at the screening/baseline visit. Visits will occur at the end of Weeks 2, 4, 8, and 12. Telephone contact will be made at Weeks 1, 6, and 10 to assess adverse events (AEs) and concomitant therapy. In addition, an optional telephone call or other form of communication will be made with the subject approximately 1 week (\pm 2 days) after the visit (e.g., at Weeks 3, 5, 7, 9, and 11) to check on status. All subjects will receive up to 12 weeks of open-label treatment in this trial.

Follow-up: Subjects will be followed for safety via telephone contact or clinic visit 21 (\pm 3) days after the last dose of open-label brexpiprazole.

See [Figure 3.1-1](#) for a schematic of the trial design.

^aThe last visit of the previous double-blind BPD trial will serve as the baseline measures for Trial 331-201-00195. If a subject is unable to rollover immediately, up to 3 days may be permitted between the end of the double-blind trial and the start of IMP in the open-label extension trial; however, this must be discussed with the medical monitor.

^bTelephone contact or clinic visit.

^cTelephone contact will be made at Weeks 1, 6, and 10 to assess AEs and concomitant therapy.

Figure 3.1-1 Trial Design Schematic

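### SAP 9.1 counts a continuing event as treatment-emergent if it was already serious or drug related, with no change needed after the first open-label dose

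*SAP*

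**What the plan says.** The primary safety endpoint is the frequency and severity of AEs in the open-label treatment phase. It is reported through TEAE tables, so the TEAE definition decides what is counted. The definition appears in four places.

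- **SAP 9.1.** The lead sentence asks for onset on or after the first dose of IMP. The next sentence elaborates and adds a limb for events already present: they count "if the event was continuous from baseline and was worsening, serious, study drug related", or if they led to death or to a change in study therapy.
- **Protocol 8.8.1.** It has the same structure, with the start point named as open-label treatment ("TEAEs are all AEs which started after start of open-label IMP treatment") and the limb "if the event was continuous from baseline and was worsening, serious, IMP related".
- **Protocol 9.4.2.1**, the statistical section on AEs. A pre-existing event counts when it is "an AE that is reported at baseline and increases in intensity or becomes serious or IMP-related", or leads to one of the listed outcomes.
- **Protocol 1.1, Synopsis.** It repeats the rule of 9.4.2.1, opening with "A TEAE is defined as an AE that starts after the first dose of IMP or an AE that is reported at baseline".

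SAP Section 1 settles precedence: "if the analyses described in the protocols differ from those in this SAP, the methods of the SAP prevail".

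**The concern.** In the SAP limb only *worsening* describes something that happens over time. *Serious* and *study drug related* describe what an event is. Protocol 9.4.2.1 and the synopsis use the verb *becomes*, which requires a change. The two forms give different answers for an event that was already serious, or already rated related, before the first open-label dose and then simply continued.

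Under the governing text such an event would be shown as having emerged on open-label brexpiprazole. Limiting the tables to the open-label phase does not remove it, because the continuing-event limb exists to admit events that began earlier. Rows for serious events usually hold few subjects, so even one carried-over event can be visible there.

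**Working it through.** No figure in the plan depends on this definition, so there is nothing to recompute. The check is to classify test events under each text.

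**Test events.** All are ongoing at the first open-label dose and lead to no death and no change in dosing.

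- A: already serious before the dose, unchanged afterwards.
- B: not serious, already rated related to IMP before the dose, unchanged afterwards.
- C: not serious before the dose, turns serious afterwards.
- D: mild before the dose, severe afterwards.

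| Text | A | B | C | D |
|---|---|---|---|---|
| SAP 9.1, lead sentence alone | no | no | no | no |
| SAP 9.1, with the continuing-event limb | TEAE | TEAE | TEAE | TEAE |
| Protocol 8.8.1, with the continuing-event limb | TEAE | TEAE | TEAE | TEAE |
| Protocol 9.4.2.1 | no | no | TEAE | TEAE |
| Protocol synopsis | no | no | TEAE | TEAE |

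The texts part only on A and B. Events that truly change (C and D) count under both forms, so requiring a change loses none of them.

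**Where A would appear.** In the SAP list of tables, A enters overall TEAE incidence (CT-8.2.1), TEAEs by severity (CT-8.2.2) and the serious-TEAE tables (CT-8.2.9, CT-8.5.1, CT-8.5.2). B enters CT-8.2.1, CT-8.2.2 and the drug-related tables (CT-8.3.1, CT-8.3.2).

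**When A or B can arise.** AE recording begins at consent for this trial (Protocol Table 1.3-1, footnote q).

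- Immediate rollover: consent is at the last double-blind visit, and the first open-label dose comes one day after the last double-blind dose (Protocol 6.1). The interval is about 1 day.
- Rollover with a permitted gap: up to 3 days.
- Delayed entry under the COVID-19 provision: consent precedes eligibility procedures (Protocol 10.1.2) and the first dose is given at a separate baseline visit. SAP 3.1 says "The screening period will be up to 21 days and may be extended upon discussion with the medical monitor".

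**How likely B is.** Causality is recorded as relationship to trial treatment, and a rating of related requires a temporal link (Protocol 8.8.1, 8.8.2). Before the first open-label dose this can happen only if a site rates the event against the parent-trial drug. B is therefore narrower than A.

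**Whether the data can show a change.** Protocol 8.8.2 lists start date, end date, seriousness, severity, relationship, action taken and outcome. It lists no date on which seriousness or relationship changed. From those fields alone a programmer cannot tell A from C. Both show a pre-dose start, a serious flag and an event still ongoing at the dose.

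**Size.** One such subject adds 1/n to a serious-TEAE incidence, where n is the Safety Sample in that parent-treatment group. The documents give neither n nor a rate of such events, so no shift can be calculated.

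**The case against.** The best defence has four parts.

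1. **The SAP follows one of two protocol versions.** Protocol 8.8.1, the section headed Definitions, uses the same form, and SAP Section 1 leaves one operative rule. This stands. A reader might infer that the SAP departs from the protocol as a whole, but the protocol disagrees with itself. It does not remove the point, because the version that governs is the looser one and differs from the protocol's own statistical section.

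2. **The list can be read as post-baseline developments.** Worsening, death and dose changes all happen after baseline, so *serious* and *related* could be taken the same way. That is a fair charitable reading, but the SAP does not state it, the protocol's statistical section shows how it would be stated, and the listed AE fields do not support it without a further recording rule.

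3. **The affected set is close to empty.** Subjects must be outpatients. Those at significant suicide or self-harm risk, or with medically significant laboratory, vital-sign or ECG findings, are excluded, as is anyone judged unsuitable. This stands as a limit on size.

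4. **The reference dose is clear enough.** The SAP does use IMP for the parent-trial drug, as where subjects "took the investigational medicinal product [IMP] through the last scheduled treatment visit". A reader might infer that *start of IMP* in SAP 9.1 could mean the first parent-trial dose, which would sweep in parent-trial events. The documents do not support that. SAP 7.1 anchors baseline to the first dose of open-label IMP, SAP 3.2 calls the parent drug double-blind IMP, and SAP 9.1 tabulates the open-label phase. Naming open-label IMP in the definition is a tidy-up, not a separate defect.

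**Conclusion.** The concern holds, at modest size. The governing definition for the primary endpoint, read literally, classifies an unchanged pre-dose event as an open-label TEAE, and as a serious or related one, which the protocol's statistical section and synopsis do not. The direction is over-counting, so harm is not hidden. The tables are descriptive, and no difference between parent-treatment groups is claimed.

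This rests on the literal reading of *was*, and on the affected events being AEs recorded between consent and the first open-label dose. The documents do not say whether AEs ongoing from the parent trial are also entered in this trial's AE record; if they are, more events could be caught.

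Three stronger inferences are not supported.

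- The longer interval for delayed-entry subjects might suggest a much larger problem in that group. Interval length is not an event count, and the number of delayed-entry subjects is not given.
- SAP 9.1 includes AEs up to 30 days after the last dose, beyond the contact at 21 ± 3 days. That is an upper limit for inclusion and misclassifies nothing. Some reporting does continue: pregnancies for at least 30 days (Protocol 10.3) and updates on immediately reportable events already known.
- The texts vary between *on or after* and *after* the first dose. The SAP lead sentence settles this.

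**What to change.** **SAP 9.1.** Replace the two sentences with one definition. A TEAE is an AE that starts on or after the first dose of open-label IMP. It is also an AE ongoing at that dose which afterwards intensifies, becomes serious, comes to be judged related to open-label IMP, or leads to death or to open-label IMP being stopped, interrupted or reduced.

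**Identifying a change.** State how it is found in the AE records, for example by entering a changed event as a new record with its own start date. If eSource instructions already cover this, cite them.

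**Unchanged carried-over events.** Put them in a separate listing, so that no safety information is lost.

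**Protocol.** Align 8.8.1, 9.4.2.1 and the synopsis at the next amendment. Because the SAP prevails, correcting SAP 9.1 puts the tables right without waiting for it.

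**Cost.** One rewritten definition, one extra listing, a recording instruction to sites if none exists, and possibly some queries on records already entered. TEAE counts may come out slightly lower.
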